1
2
3
4
5
6
7 **A Multi-Centered, 2-Period, Randomized Crossover Study to Assess the**
8 **Efficacy of Predictive Low Glucose Suspend versus Sensor-Augmented**
9 **Pump Therapy in the Management of Type 1 Diabetes**

10
11 **Tandem PLGS Pivotal Study**

12
13 **Statistical Analysis Plan**
14 **Randomized Crossover Trial**

15
16
17
18
19 Version 1.2
20 Version Date: 1/22/2018
21 Author: [name]
22 Protocol Version: 5.0

23
24
25
26
27
28
29 *Note: The table shells are included in a separate document.*

Revision History

The following table outlines changes made to the Statistical Analysis Plan.

Version Number	Author	Senior Statistician	Effective Date	Study Stage	Revision Description
1.0	[name]	[name]	1/11/2017	Enrollment	Original Version
1.1	[name]	[name]	1/18/18	Enrollment	Added more protocol adherence metrics and system usability questionnaire
1.2	[name]	[name]	2/2/18	Data closeout	Removed “procedural deviations” tabulations, edited basal insulin calculation wording, and re-defined a ketosis event.

30 Author:

31

32

33

34

35 Senior Statistician:

36

37

38

39

40 Principal Investigator:

41

42
43 This document outlines the statistical analyses to be performed for the Tandem PLGS Pivotal study. The
44 approach to sample size and statistical analyses for this study are summarized below.
45

46 **1. Study Overview**

47 This is a multicenter, randomized, two-period crossover study to assess the efficacy and safety of a
48 Predictive Low-Glucose Suspend system (PLGS) in comparison with Sensor-Augmented Pump therapy
49 (SAP) in T1D patients \geq 6 years old. Enrollment will target 90 participants. All participants will receive
50 both interventions, and the order of receiving them will be randomized based on a 1:1 ratio.
51

52 Following screening, the study includes 5-13 clinic visits and 4-10 phone/email/text contacts for subjects
53 completing the study. The training phases immediately following screening (pre-randomization) will
54 consist of 10-14 days for CGM training and 14-28 days for SAP training. Either CGM Training or both
55 training phases may be skipped at an investigator's discretion based on device use status per protocol.
56 Randomization will be preceded by a 10-day pilot period where data collected from this period will be
57 evaluated for system usability and predetermined safety metrics before participants \geq 12 years of age
58 may be randomized into the crossover trial. Immediately after randomization, subjects will enter the two
59 3-week study periods (21 days each) and will test one intervention per study period, using either the
60 PLGS or SAP system first. The interventions will not be separated by a washout period.
61

62 **2. Statistical Hypotheses**

- 63 • *Null Hypothesis*: There is no difference in the mean time spent below 70 mg/dL over the 21-day
64 period between the two treatment groups.
- 65 • *Alternative Hypothesis*: There is a nonzero difference in the mean time spent below 70 mg/dL
66 over the 21-day period between the two treatment groups.
67

68 **3. Sample Size**

69 The study is projected to include at least 90 subjects. Of these study participants, at least 45 will be $<$ 18
70 years old, and at least 45 will be \geq 18 years old. Of the 45 participants that are $<$ 18 years old, at least 15
71 participants will be 12 to 17 years old, and at least 15 will be 6 to 11 years old. The 90 study participants
72 will also include a minimum of 15 pump users, 15 multiple daily injection of insulin (MDI) users, 15
73 CGM naïve users (may be pump or MDI users), and 15 experienced CGM users (may also be pump or
74 MDI users).
75

76 The subjects will be randomized to the order of the interventions based on a 1:1 ratio. Randomization
77 will not be stratified.
78

79 **4. Outcome Measures**

80 **4.1 Primary Efficacy Endpoint:**

81 Percent of CGM glucose sensor values < 70 mg/dL

83 **4.2 Secondary Efficacy Endpoints:**

84 *CGM Metrics*

85 Overall Glucose Control

86 1) Mean of CGM glucose sensor values

87 2) Percent of CGM glucose sensor values between 70 and 180 mg/dL (not inclusive of the
88 limits)

89 Hypoglycemia

90 3) Percent of CGM glucose sensor values < 60 mg/dL

91 4) Percent of CGM glucose sensor values < 50 mg/dL

92 5) Area over curve for CGM glucose sensor values < 70 mg/dL.

93 6) Low blood glucose index (LBGI).

94 7) Frequency of CGM-measured hypoglycemic events per week (see below)

95 Hyperglycemia

96 8) Percent of CGM glucose sensor values > 250 mg/dL

97 9) Percent of CGM glucose sensor values > 180 mg/dL

98 10) Area under curve for CGM glucose sensor values > 180 mg/dL.

99 11) High blood glucose index (HBGI)

101 **4.3 Calculation of CGM Metrics**

102 Each metric will be calculated for CGM sensor values over the entire 24-hour period.

103

104 Primary Outcome - % Time Below 70 mg/dL

105 The percentage of glucose sensor values <70 mg/dL will be calculated for each participant in each 3-
106 week treatment period by pooling all glucose sensor readings that occur within each 3-week period.

107 Available CGM data will be included in the calculation based on when the subject completes the study
108 visits. If exact date-times of when patient left the clinic on study period initiation visits are available,
109 then the study windows for CGM data inclusion are defined as:

111

	Includes All Available CGM data from:	
	Start Date	Last Date
Period 1	Date-time in which patient left clinic on Period 1 Initiation Visit	Earlier of: a) Date-time in which patient left clinic on Period 1 Initiation Visit + 21 full days, or b) Date-time in which patient left clinic on Period 2 Initiation Visit
Period 2	Date-time in which patient left clinic on Period 2 Initiation Visit	Earlier of: a) Date-time in which patient left clinic on Period 1 Initiation Visit + 21 full days, or b) Final Visit

112

113 Otherwise, in the case of a protocol deviation and the above information is not available, the study windows are defined as:

115

	Includes All Available CGM data from:	
	Start Date	Last Date
Period 1	Randomization Visit +1	Earlier of: a) Randomization Visit + 22 Days, or b) Period 2 Initiation Visit
Period 2	Period 2 Initiation Visit +1	Earlier of: a) Period 2 Initiation Visit + 22 Days, or b) Final Visit

116

117 All glucose sensor readings will be weighted equally in the pooled percentages regardless of how they distribute across weeks. Data will not be truncated due to protocol deviations.

119

120 **Secondary CGM Metric Outcomes**

121 All secondary CGM metrics will be calculated analogously as described above for the primary outcome.

122

123 **PLGS and CGM Use**

124 Number of hours of CGM/PLGS use per week will be calculated as the sum of the time intervals between readings, excluding calibration readings. If an actual time interval is greater than the device's default time interval, then that time interval will be set to the device's default time interval. Number of hours of CGM and PLGS use will be expressed as a percentage of the total number of hours in a week.

128

129 Total percentage of time PLGS and CGM is used per week will be calculated by dividing the total number of hours of PLGS readings by the maximum possible number of hours within the study period visit dates described above. Number of days of PLGS and CGM use per week is calculated as the count

132 of days during the week where there was at least one PLGS/CGM reading. Data from both study periods
133 will be included in this analysis. No missing data will be imputed.

134

135 **Hypoglycemic Events**

136 A CGM-measured hypoglycemic event will be defined as:

- 137 • at least 2 sensor values < 54 mg/dl
- 138 • that are 15 or more minutes apart
- 139 • no intervening values > 54 mg/dl
- 140 • Event ends when:
 - 141 ➤ at least 2 sensor values > 70 mg/dl
 - 142 ➤ that are 30 or more minutes apart
 - 143 ➤ no intervening values < 70 mg/dl
- 144 • Participant becomes eligible for a new event as soon as the above criteria for ending the previous
145 event have been met.

146

147 **5. Description of Statistical Methods**

148

149 **5.1 General Approach**

150 All analyses will compare the 3-week period of PLGS to the 3-week period of SAP and will follow the
151 intention-to-treat principle with each period analyzed according to the treatment assigned by
152 randomization regardless of actual PLGS or SAP utilization. All participants who have at least one
153 CGM reading in each 3-week period will be analyzed for the primary and secondary outcomes. All p-
154 values will be two-sided.

155

156 Standard residual diagnostics will be performed for all analyses. If values are highly skewed, then a
157 transformation or nonparametric methods will be used instead. Previous experience suggests that a
158 transformation may be necessary for the hypoglycemic and hyperglycemic outcomes. We do not expect
159 that a transformation will be necessary for some overall glucose control metrics (such as mean glucose).

160

161 **5.2 Analysis Cohorts**

- 162 • All randomized participants who have at least one CGM reading in both 3-week periods will be
163 analyzed for the Intention-to-Treat (ITT) Analysis with each day included in the treatment group
164 assigned by randomization.
- 165 • Safety outcomes will be reported for all enrolled participants, irrespective of whether the study was
166 completed.
- 167 • A per-protocol analysis will be restricted to participants with ≥ 200 hours of CGM data in each 3-
168 week period. This analysis will only involve the primary outcome, and will only be done if at least
169 10% of subjects are excluded based on this criterion.

170

171 **6. Analysis of the Primary Efficacy Endpoint**

172

173 **6.1 Included Subjects**

174 As noted in section 5.2, the primary analysis for this study will include all randomized subjects with at
175 least one CGM sensor reading in each of the two treatment periods. No additional minimum amount of
176 CGM use is required otherwise.

177

178 **6.2 Missing Data**

179 There will be no imputation of missing CGM data for the primary analysis in this study.

180

181 **6.3 Statistical Methods**

182 Mean \pm SD (standard deviation) or summary statistics appropriate to the distribution will be reported for
183 % time below 70 mg/dL for each treatment arm. A repeated measures regression model with an
184 unstructured covariance structure will be fit for percent time below 70 mg/dL to compare the two
185 treatments. The model will adjust for period as a covariate.

186

187 Residual values from the above model will be examined for an approximately normal distribution. It is
188 likely that the residuals themselves will have a skewed distribution, but that the paired differences from
189 the same subject may follow an approximate bell-shaped curve. However, if the paired differences have
190 a skewed distribution, then an appropriate transformation or a nonparametric analysis based on ranks
191 will be performed. Significance will be assessed at the 5% level.

192

193 A carryover effect is not expected, but it will be assessed with a separate model built with the inclusion
194 of a period by treatment interaction. However, the study is not expected to have sufficient power in
195 making definitive conclusions about the period by treatment interaction.

196

197 **7. Analysis of the Secondary Endpoints**

198 The same subjects will be included as in the primary analysis. Missing data will not be imputed for any
199 of the secondary analyses in this study.

200

201 **7.1 Statistical Methods**

202 For all secondary outcomes, summary statistics appropriate to the distribution will be tabulated by
203 treatment group. Analysis of all secondary endpoints will parallel the primary analysis. A ranked normal
204 score transformation will be applied to all highly skewed secondary outcomes.

205

206 **7.2 Secondary Analyses by Time of Day**

207 Each of the secondary outcomes will be calculated separately for sensor values during daytime (6:00
208 AM to just before 10:00 PM) and sensor values during nighttime (10:00 PM to just before 6:00 AM).

209 The primary outcome, percentage of glucose sensor values < 70 mg/dL, will also be divided into
210 daytime and nighttime periods as an additional secondary outcome.
211
212 For all secondary outcomes separated by time of day, summary statistics appropriate to the distribution
213 will be tabulated by treatment group. The same model described above for the primary and secondary
214 analyses will be fit with the inclusion of a treatment by time of day interaction. The p-value for the
215 interaction term will be reported. These analyses will be conducted to determine whether a similar trend
216 to the overall treatment effect is seen in the different times of day. An appropriate transformation or a
217 nonparametric analysis based on ranks will be applied to all highly skewed secondary outcomes.
218
219 The study is not expected to have sufficient statistical power for definitive conclusions in the secondary
220 analyses by time of day, and statistical power will be low to formally assess a treatment by time-of-day
221 interaction. Interpretation of the analyses by time of day will depend on whether the overall analysis
222 demonstrates a significant treatment effect. In the absence of any significant treatment effects in the
223 overall analyses, assessment of secondary analyses by time of day will be considered exploratory and
224 used to suggest hypotheses for further investigation in future studies.
225

226 **8. Safety Analyses**

227

228 Safety outcomes will be tabulated by participant for all adverse events from enrollment to the final study
229 visit or final adverse event, whichever comes later.
230

231 **8.1 Definitions**

232 Reportable adverse events for this protocol include severe hypoglycemia (SH), diabetic ketoacidosis
233 (DKA), and any other untoward medical occurrence that meets criteria for an adverse event (AE) or
234 serious adverse event (SAE). Device deficiencies that could have led to an adverse device effect will
235 also be reported.
236

237 Hypoglycemic events will be considered severe if the participant required assistance from another
238 person to actively administer carbohydrate, glucagon, or engage in other resuscitative actions. This
239 means that the subject is impaired cognitively to the point that he/she is unable to treat him- or herself, is
240 unable to verbalize his or her needs, is incoherent, disoriented, and/or combative, or experiences seizure
241 or coma. If plasma glucose measurements are not available during such an event, neurological recovery
242 attributable to the restoration of plasma glucose to normal is considered sufficient evidence that the
243 event was induced by a low plasma glucose concentration.
244

245 Definite DKA is defined by the Diabetes Control and Complications Trial (DCCT) as having all of the
246 following:
247

- Symptoms such as polyuria, polydipsia, nausea, or vomiting

- 248 • Serum ketones > 1.5 mmol/L or large/moderate urine ketones
249 • Either arterial blood pH < 7.30 or venous pH < 7.24 or serum bicarbonate < 15
250 • Treatment provided in a healthcare facility

251

252 **8.2 Adverse Events Summary**

253 All episodes of SH, DKA, unanticipated adverse device effects, and any other reportable adverse events
254 will be listed by treatment group. For each event, the following information will be reported:

- 255 • Onset date of the event
256 • Resolution date of the event
257 • Duration of the event
258 • Phase of the trial (run-in phase, pilot period, PLGS phase, or SAP phase)
259 • Description of the event
260 • Intensity of the event
261 • Seriousness of the event
262 • Whether the event was related to the study treatment
263 • Whether the event was related to the study procedure
264 • Whether the event was related to the study device
265 • Whether the event required treatment
266 • Outcome of the event

267

268 Any adverse events that occurred before the randomization visit (i.e., during the run-in or pilot phase)
269 will be tabulated in separate pre-randomization tables in the same manner as the post-randomization
270 adverse events.

271

272 **8.3 Comparison of Safety Outcomes between Treatment Groups**

273 Due to the short duration of the study, it is not anticipated that there will be enough DKA, SH, ketosis (a
274 calendar day with at least one instance of blood ketone level > 1.0 mmol/L), unanticipated adverse
275 device effects, or any other reported adverse events for a formal statistical comparison of the treatment
276 arms. If there are enough events, the following analyses will be performed.

277

278 For each of the following safety outcomes, mean \pm SD or summary statistics appropriate to the
279 distribution will be tabulated by treatment group:

- 280 • Number of subjects with any DKA events
281 • Number of episodes of DKA events per subject and incidence rate per 100 person years
282 • Number of subjects with any SH events
283 • Number of episodes of SH events per subject and incidence rate per 100 person years
284 • Number of subjects with any ketosis events
285 • Number of episodes of ketosis events per subject and incidence rate per 100 person years

- 286 • Number of subjects with any unanticipated device effects
287 • Number of unanticipated device effects per subject and incidence rate per 100 person years
288 • Number of subjects with any other reported adverse events
289 • Number of other reported adverse effects per subject and incidence rate per 100 person years
290

291 All of the above safety outcomes will be tabulated for all subjects (including dropouts and withdrawals),
292 regardless of whether CGM data are available or whether the device was operational. Any adverse
293 events that occurred before the randomization visit (i.e., during the run-in or pilot phase) will not be
294 included in the rate calculations or treatment group comparisons listed above.
295

296 The number of person-years for the calculation of incidence rates will be defined as the number of
297 person-years from the randomization visit to the last visit date or adverse event date, whichever is later.
298

299 For each of DKA, SH, ketosis, unanticipated adverse device effects, and all other reported adverse
300 events, if there are enough events, rates will be compared using a repeated measures Poisson regression
301 model adjusting for period.
302

303 9. Adherence and Retention Analyses

304

305 9.1 Amount of PLGS and CGM Usage

306 The amount of PLGS and CGM use in hours per week and days per week will be tabulated for each
307 treatment arm (PLGS use will only be for the PLGS arm).
308

309 Summary statistics appropriate to the distribution and range will be reported by treatment group for the
310 days per week and percentage of hours per week of CGM and PLGS use. The percentage of time per
311 week of CGM use will be compared between treatments using the same model described above for the
312 primary outcome.
313

314 Amount of PLGS and CGM usage will further be tabulated by daytime and nighttime (as defined
315 above), but no formal statistical comparison will be made.
316

317 9.2 Protocol Adherence

318 The following tabulations and analyses will be performed to assess protocol adherence for the study:

- 319 • Number of protocol deviations by severity with descriptions of each deviation instance
320 • Number of unscheduled visits and reasons for each unscheduled visit instance
321 • Number of device issues and descriptions of each instance
322

323 Tabulations and analyses will be divided into pre- and post-randomization stages where possible. For
324 post-randomization stages, tabulations and analyses will be further divided into treatment groups. In
325 addition, the following flowcharts will be produced:

- 326
- 327 • Flow chart accounting for all subjects at all visits post-randomization to assess visit completion
328 rates
 - 329 • A flow chart accounting for the number of subjects enrolled, the number of subjects who
330 completed the run-in phase, the number of dropouts pre- and post-randomization, and the
331 number of subjects eligible to be included in the primary analysis

332

333 **10. Baseline Descriptive Statistics**

334 Baseline demographic and clinical characteristics of the study cohort will be summarized in a table in
335 addition to baseline CGM metrics. Baseline CGM data will be taken as follows from the home use, and
336 SAP training phases (details above in Section 1):

337

- 338 • If subject was required to go through SAP Training, then baseline CGM data from the SAP
339 Training period will be used.
- 340 • If subject was allowed to skip both CGM and SAP Training, then baseline CGM data from 28
341 days of home use prior to enrollment will be used.

342

343 The following descriptive statistics will be tabulated overall and by randomization group:

344

- 345 • Age in years
- 346 • Gender
- 347 • Race
- 348 • Type I diabetes duration in years
- 349 • BMI (if available)
- 350 • HbA1c (% mmol/L)
- 351 • Baseline CGM Metrics
- 352 • Current insulin modality
- 353 • Past amount of pump use for patients using pump at enrollment
- 354 • Daily insulin units (total, basal, and bolus)
- 355 • CGM use status at enrollment
- 356 • Days of CGM use in the past month at enrollment
- 357 • Daily insulin units
- 358 • Time range of most recent severe hypoglycemic event
- 359 • Number of severe hypoglycemic events in the last 12 months
- 360 • Number of severe hypoglycemic events involving seizure/coma over lifetime

- Number of severe hypoglycemic events involving seizure/coma in the last 12 months
- Time range of most recent DKA event
- Number of DKA events in the last 12 months
- Number of glucose tests per day
- Other non-insulin blood sugar control medications taken

For continuous variables, summary statistics appropriate to the distribution will be given. For discrete variables, number and percentage will be reported for each category.

11. Planned Interim Analyses

The purpose of the interim analysis is to re-estimate sample size in the case that the overall rate of hypoglycemia (% time below 70 mg/dL) in the control (SAP) arm is significantly less than what was assumed in the original sample size calculation. Only CGM data from baseline and the SAP arm will be used. The analyses will be masked to the PLGS data. No assessment of efficacy with the PLGS arm is to be made, and thus there will be no inflation of type 1 error rate.

With the planned sample size of 90, the original calculation estimated statistical power >99% to detect a 33% relative reduction assuming the control arm hypoglycemia is 4.0% using a two-tailed test with the type 1 error rate at 5%. The goal of this interim analysis is to assess whether the 4.0% assumption used in the original calculation was approximately correct, and if not whether the sample size needs to be modified. The interim analysis will be conducted when the 90th subject is enrolled into the screening phase. All partial data from all non-dropped subjects with either baseline or post-randomization CGM data will be included. Baseline CGM data will be taken as specified in Section 10, and all post-randomization data up to the final study period date will be included.

Study Stage Completed ^a	Rough Projection for # Subjects at Interim Analysis
CGM data from pre-randomization run-in ^b	N=90
Completed \geq 1 weeks of Period #1	N=45 (~22 or 23 randomized to control-first)
Completed Period #1	N=22 (~11 randomized to control-first)
Completed \geq 1 weeks into Period #2	N=0 (but possible if slower recruitment)
Completed Period #2	N=0 (but possible if slower recruitment)

^a Each row denotes a subset of subjects in the row above it.

^b Taken as specified in the table in section 10

A repeated measures model controlling for study stage will be run with 1-3 data values per subject depending on which stage of the study (as categorized in the table above) was completed by the subject at the time of the interim analysis. This model will be used to estimate the amount of hypoglycemia in the control arm utilizing information from both the baseline and the control arm of the RCT phase. Any

393 data from a participant's PLGS study period will be excluded. The assumption is that the amount of
394 hypoglycemia from the baseline will be reasonably well-correlated with the amount in the control arm
395 during the RCT phase.

396
397 Hypoglycemia, or percent of time glucose is below 70 mg/dL, from each of the study stages in the table
398 will be calculated as specified in Section 4.3. If the overall estimated time below 70 mg/dL is <4%, then
399 we will take the adjusted sample size to be:

400
401 $52 * 4\% / \text{estimated hypoglycemia rate in control arm}$

402 where the estimated rate in the denominator is calculated from the model described above. If the
403 estimated rate of hypoglycemia is so low that even 150 subjects would provide little power, then we will
404 stay with the originally planned 90.

405 **12. Subgroup Analyses**

406 Subgroups will be defined by:

- 407
- 408 • Age (grouped by < 18 years and \geq 18 years)
 - 409 • Type 1 diabetes duration (split into 2 groups with cutpoint approximately at the median)
 - 410 • Baseline HbA1c (grouped by < 8.0% and \geq 8.0%)

411 Mean \pm SD or summary statistics appropriate to the distribution will be reported for % time below 70
412 mg/dL for each treatment arm in each subgroup. These analyses are considered exploratory and are not
413 being evaluated as independent hypothesis tests.

414 **13. Multiple Comparisons/Multiplicity**

415 The primary analysis involves a single treatment arm comparison for a single outcome measure so no
416 correction for multiple comparisons will be performed.

417 For the secondary analyses, the false discovery rate (FDR) will be controlled using the adaptive
418 Benjamini-Hochberg procedure for multiple comparisons. The FDR corrections will be done separately
419 for the following categories:

- 420 • Secondary Efficacy Outcomes and CGM Usage
- 421 • Secondary Efficacy Outcomes by Time of Day
- 422 • Miscellaneous (CGM Usage and Insulin Analyses)

423 Safety analyses will not be included in the multiple comparison corrections.

424 **14. Exploratory Analyses**

425 No additional exploratory analyses are planned.

431

432 15. Additional Analyses

433 The following outcomes will be tabulated separately over a 24-hour period, daytime, and nighttime
434 where applicable:

- 435 • Insulin delivery per treatment group, including total insulin units per day, basal insulin units
436 per day, and bolus insulin units per day.
- 437 • PLGS group only: Frequency of insulin suspension events and duration of events per subject-
438 day, including individual suspensions and cumulative suspension time
- 439 • PLGS group only: CGM glucose nadir during suspension events and peak within 2 hours
440 after events.

441

442 Mean \pm SD or summary statistics appropriate to the distribution will be reported for each of these
443 outcomes. Insulin delivery will be compared between treatments using the same model described above
444 for the primary outcome.

445

446 Total basal insulin is recorded as an hourly cumulative running total of the amount of basal insulin
447 delivered for each day. Total basal insulin will be calculated by a summation of the increments between
448 the cumulative counts for each day, not including days where the insulin pump was reset or days where
449 a time change caused basal readings to overlap. Total bolus will be calculated by summing all non-
450 missing bolus delivery amounts recorded by the insulin pump for each period.

451

452 App-Based Monitoring and Intervention Questionnaire

453 Visits in which participant took carbs or insulin to correct blood glucose in response to a commercially-
454 available CGM monitoring app will be tabulated by treatment group. The questions are answered at
455 every visit past the first study period's initiation visit, and include any carbs or insulin taken since the
456 last visit or contact. Responses are a binary yes/no. Summary statistics tabulated will include number
457 and percentage of a) participants taking carbs and b) participants taking insulin at each visit/contact. The
458 analysis cohort for all of these additional analyses are the same as the primary analysis. Data from both
459 study periods (defined in section 4.3) will be included in this analysis. No missing data will be imputed.

460

461 System Usability Questionnaire

462 This 10-item questionnaire is given at the end of every participant's PLGS study period to determine
463 system usability of the PLGS feature:

464

465

Question

1. I think that I would like to use this system frequently
2. I found the system unnecessarily complex
3. I thought the system was easy to use
4. I think that I would need the support of a technical person to be able to use this system
5. I found the various functions in this system were well integrated
6. I thought there was too much inconsistency in this system
7. I would imagine that most people would learn to use this system very quickly
8. I found the system very cumbersome to use
9. I felt very confident using the system
10. I needed to learn a lot of things before I could get going with this system

466

467 Responses are ranked on a 5-point scale from 1 (strongly disagree) to 5 (strongly agree). For item 1, 3, 5,
468 7, and 9, each participant's response is scored by taking the response ranking and subtracting 1. For
469 items 2, 4, 6, 8, and 10, each participant's response is scored by subtracting the response ranking from 5.
470 Higher scores denote better perceived usability. Composite scores are calculated by taking the sum of
471 the individual item scores from each participant and multiplying by 2.5. Possible composite scores range
472 from 0 to 100, with higher scores denoting better perceived usability.

473

474 Summary statistics appropriate to the distribution will be tabulated for each individual item and for the
475 composite score.

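### The main window table in SAP 4.3 ends Period 2 at 21 days after the start of Period 1, so as written it gives no usable 3-week Period 2 value for the primary endpoint

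*SAP*

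**What the plan says.** SAP 4.3 (Primary Outcome) has two window tables. The first applies when the exact times at which participants left the clinic are available. The second is a fallback for protocol deviations in which those times are missing.

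- **First table, Period 1:** runs from departure at the Period 1 Initiation Visit to the earlier of 21 full days later or departure at the Period 2 Initiation Visit.
- **First table, Period 2:** starts at departure from the Period 2 Initiation Visit and ends at "Earlier of: a) Date-time in which patient left clinic on Period 1 Initiation Visit + 21 full days, or b) Final Visit".
- **Fallback table, Period 2:** starts the day after the Period 2 Initiation Visit and ends at "Earlier of: a) Period 2 Initiation Visit + 22 Days, or b) Final Visit".

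SAP Section 1 describes "3-week study periods (21 days each) and will test one intervention per study period", with no washout between them. For the other CGM outcomes, SAP 4.3 states: "All secondary CGM metrics will be calculated analogously as described above for the primary outcome". The percentage of device use is obtained by dividing "by the maximum possible number of hours within the study period visit dates described above".

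On cohorts, SAP 5.2 reads "All randomized participants who have at least one CGM reading in both 3-week periods will be" included in the ITT analysis, and "A per-protocol analysis will be restricted to participants with ≥ 200 hours of CGM data" in each period.

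**The concern.** Limb (a) of the Period 2 end date repeats limb (a) of the Period 1 row. Because Period 2 begins when Period 1 ends, about three weeks in, a cut-off 21 days after the start of Period 1 falls at or before the start of Period 2 for anyone crossing over on schedule or late.

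This rule chooses the readings for the sole primary endpoint. It also decides who is analysed, since a participant needs at least one reading in each period and missing CGM data are not imputed (SAP 6.1 and 6.2). The secondary CGM metrics take the same windows, and the device-use denominator appears to. In SAP 15, the app-monitoring questionnaire cites the Section 4.3 periods directly, and the additional analyses there share the primary-analysis cohort, which these windows determine.

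**Working it through.** **Inputs**

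- Period length: 21 days (SAP 1).
- One sensor reading every 5 minutes (Protocol 1.2), so 288 per day.
- End-of-period visit: day 21 to 28 (Protocol Table 1, 21+7d) or day 14 to 28 (Protocol 5.5, 21 ± 7 days). The end of Period 1 is the crossover visit.
- Per-protocol minimum: 200 hours per period (SAP 5.2).

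**Intended size.** 21 × 24 = 504 hours, and 21 × 288 = 6,048 readings per period.

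**Formulas.** Let departure at Period 1 start be time 0, crossover departure be v days later, and the Final Visit be day F.

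- Period 1 = min(21, v).
- Period 2 as written = max(0, min(21, F) − v).
- Period 2 anchored on its own start = min(v + 21, F) − v.

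With visits inside either window, F is at least 14 + 14 = 28. Limb (b) therefore never comes first, and the as-written length reduces to max(0, 21 − v). The Period 1 row does give the intended 21 days whenever v ≥ 21.

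| v (days) | Period 1 | Period 2 as written | Period 2 re-anchored* |
|---|---|---|---|
| 14 | 14 d | 7 d = 168 h = 2,016 readings | 21 d |
| 17 | 17 d | 4 d = 96 h = 1,152 readings | 21 d |
| 20 | 20 d | 1 d = 24 h = 288 readings | 21 d |
| 20.8 | 20.8 d | 0.2 d = 4.8 h, about 58 readings | 21 d |
| 21 | 21 d | 0 | 21 d |
| 24 | 21 d | 0 (end falls 3 d before start) | 21 d |
| 28 | 21 d | 0 (end falls 7 d before start) | 21 d |

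*Assumes the Final Visit is at least 21 days after crossover. If it comes at 14 days, the window is 14 days.

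The 20.8-day row is an assumed example: a participant who leaves the day-21 visit 4.8 hours earlier in the day than at Period 1 start.

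**Per-protocol check.** 200 / 24 = 8.33 days, so 21 − v ≥ 8.33 requires v ≤ 12.67. That is earlier than day 14, the earliest visit in either window. No participant handled by the first table and crossing over within a visit window could reach 200 hours in Period 2.

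**Fallback table.** It runs from Period 2 Initiation + 1 to + 22 days, and 22 − 1 = 21 days. Read literally, the only participants with a full Period 2 would be those whose departure times were missing because of a protocol deviation.

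**The case against.** The best counter-argument is that this is a slip with only one sensible reading. The SAP overview, the hypotheses, the general approach and Protocol 10.6 all describe 3-week periods, and the fallback table has the right anchor. An analyst is not being offered two plausible rules, so the row opens no route to selective analysis. Literal coding would also show itself, because the participant flow chart and the CGM-use tables (SAP 9) would reveal an almost empty Period 2. Design, model, alpha and sample size are untouched. The interim estimate is barely affected, since SAP 11 projects no participants one week or more into Period 2 at that point.

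All of that stands, and it limits the likely harm. Some details also need care:

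- The 168-hour case depends on Protocol 5.5, which conflicts with Table 1.
- The SAP names protocol version 5.0, while the visit windows used here come from version 6.0.
- The device-use denominator refers to visit dates, so its dependence on the faulty limb is likely, not certain.

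None of this makes the row correct. A program that follows the SAP gives no valid Period 2 result, and a program that gives the valid result departs from the SAP on the primary endpoint. Version 1.2, written at data closeout, still carries the row, and its revision notes do not mention it.

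**Conclusion.** The concern holds and must be fixed. Under the first table, Period 2 has length max(0, 21 − v) days: nothing for crossovers 21 to 28 days after Period 1 start, and at most 168 of 504 hours for a day-14 crossover, set against a 14-day (336-hour) Period 1. No visit timing allowed by either protocol passage yields three weeks.

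The arithmetic rests on the table as printed and on the protocol's visit windows. How many participants crossed over before 21 days cannot be told from the documents, so neither can the number who would keep a fragment of Period 2. This is a finding about the written rule. The documents do not show how the analysis was programmed.

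**What to change.** In the first window table of SAP 4.3, change limb (a) of the Period 2 end so that it counts 21 full days from departure at the Period 2 Initiation Visit. That restores a window of min(21, F − v) days, in line with the Period 1 row and the fallback table's anchor. Record it in a dated SAP revision, and confirm that the analysis program and any independent validation program use this anchor.

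The cost is one line of text and a program check, with no extra participants and no change to study conduct.

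Separately, the end-of-period visit windows in Protocol Table 1 and Protocol 5.5 should be reconciled. The anchor error does not depend on which of them applies.
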